4 STUDY DESIGN

4.1 Overall Design

This is a randomized, evaluator-blind, single-centre, two treatment regimen (test product 1 and test product 2), controlled (standard cleanser soap use only), split-body (left and right; side of the face and lower legs), parallel group clinical study designed to evaluate the impact of 4-weeks of twice-daily topical application of two developmental moisturizing cream formulations on skin barrier function in healthy subjects with dry, sensitive skin on the face and lower legs.

The chosen application sites are the face and the lower legs. The legs will be designated right and left, and the face will be split to right or left side.

There will be two treatment regimens included in this study;

- Treatment Regimen 1 = Test Product 1 + Standard Soap
- Treatment Regimen 2 = Test Product 2 + Standard Soap

Protocol Number: 209638 Draft Clinical Protocol

Subjects will be randomized to one of these two treatment regimens. Subjects will be further randomized to have their treatments within regimen randomized to Left and Right side. Subjects will apply their allocated moisturizer to the designated side, per the randomization, the same side of the face and the same leg (left or right) will be used throughout.

Subjects will give their written informed consent prior to any study procedures taking place.

Healthy female volunteers aged 18 to 65 with self-reported dry and sensitive skin on their face and very dry skin on their legs will be recruited for this study.

To confirm whether subjects have sensitive skin they will be required to answer "yes" to the following inclusion criteria question: "Do you consider yourself to have dry, sensitive skin on your face and very dry skin on your legs?".

To confirm (per Appendix 1) whether subjects have dry skin on **both sides of their face** at the screening visit (Visit 1) and baseline visit (Visit 2) they will:

- Self-assess the feeling of tightness they are currently experiencing on each side of the face (scale range 0-4);
- Undergo dermatologist assessment of dullness, scaling and roughness on each side of the face (scale range 0-4 for each parameter).

The sum of the subject self-assessment and dermatologist assessment scores for each side of the face will be calculated. The total possible score for each side of the face is 16.

To be eligible to participate in this study, a subject must:

- Have a total score of ≥ 3 for each side of the face;
- Have no more than a 0.5-unit difference in total score between each side of the face;
- Have a dermatologist score of ≥ 1 (slight) for roughness for each side of the face;
- Have no scores of 4 (very severe) for tightness, dullness, scaling or roughness.

To confirm (per Appendix 1) whether subjects have very dry skin on **both their legs** at the screening visit (Visit 1) and Baseline visit (Visit 2) they will:

• Undergo dermatologist assessment of dullness, scaling and roughness on both legs (scale range 0-4 for each parameter).

The sum of the dermatologist assessment scores for each leg will be calculated. The total possible score for each leg is 12.

To be eligible to participate in this study, a subject must:

- Have a total score of ≥6 for each leg;
- Have no more than a 1-unit difference in total score between each leg;
- Have no scores of 4 (very severe) for dullness, scaling or roughness.

Subjects considered eligible to participate in the study will undergo a 5 to 7-day washout period, during which only the standard soap will be used on the face and legs as a standard cleanser. Subjects will be instructed to use the standard soap to cleanse the face and lower legs, as needed. Subjects will be provided a paper diary to complete during the washout period to record compliance with the soap use. This standard soap will also be used throughout the study.

At the baseline visit (Day1/Visit 2), after completion of the washout period, subjects who are deemed eligible to continue in the study will be randomized to one of the two treatment regimens. Baseline instrumental assessments of TEWL and skin moisturization (using a Corneometer) will be taken before prior to any test product application (moisturizer). Study staff will dispense study products and product use diary cards to subjects. First application of

Protocol Number: 209638 Draft Clinical Protocol

[figure not shown]
study product will be supervised by the study site staff. Subjects will be instructed to apply their assigned study product (moisturizer) to the designated side of the face and leg. Instrumental measurement of skin moisturization (using a Corneometer) will be performed at 30 minutes and 6 hours following the first single product application.

A total of 8 areas will be assigned to each subject:

Two areas on each side of the face, at the cheekbone between the nose and ear, will be assigned as close together as possible, without overlap, for all facial measurements of TEWL and moisturization as indicated in Figure 4-1:

- Area 1 (right face) and 2 (left face) will be the site used for face TEWL and Corneometer assessments throughout the treatment phase (Days 1 to 29) and the regression period (Days 29-34);
- Area 3 (right face) and 4 (left face) will be the site used for the face tape-strip challenge at Day 29.

Figure 4-1 Layout of Test Areas (Face):

Face:

AREA 1 and 2 - TEWL and corneometry assessments throughout only

[figure not shown]
AREA 3 and 4 – D-Squame challenge location only

Two areas on the outside of each lower leg assigned below each knee and above each ankle will be assigned as close together as possible, without overlap, for all leg measurements of TEWL and moisturization as indicated in Figure 4-2:

- Area 5 (right leg) and 6 (left leg) will be the site used for leg TEWL and Corneometer assessments throughout the treatment phase (Days 1 to 29) and the regression period (Days 29-34);
- Area 7 (right leg) and 8 (left leg) will be the site used for the leg tape-strip challenge at Day 29.

Protocol Number: 209638 Draft Clinical Protocol

Figure 4-2 Layout of Test Areas (Leg):

Lower Leg:

AREA 5 and 6 - TEWL and corneometry assessments throughout only

AREA 7 and 8 – D-Squame challenge location only

Subjects will return to the site on Day 2 (Visit 3), 24 hours (± 1 hr) after first single product application on Day 1, without applying any products (no cleansing/standard soap use or study product application) at home since the first supervised use. Subjects will be permitted to wash their face and legs with tap water only as needed, but not within 2 hours of the visit time. Instrumental measurement of skin moisturization (using a Corneometer) will be performed at 24 hours (± 1 hr) after first single product application on Day 1.

Second application of study moisturizer will be performed under site supervision following completion of the Corneometer measurements at Day 2 (Visit 3).

Subjects will be instructed to cleanse with the standard soap and continue to apply their study product (moisturizer) to the randomly designated side of the face and leg, twice-daily (in the morning and evening, approximately 8-12 hours apart), for 4 weeks (28±2 days).

There will be no cleansing/standard soap use or study product application in the morning of each of the assessment study site visits (i.e. visits 3, 4, and 5) of the treatment phase. Subjects will be permitted to wash their face and legs with tap water only as needed, but not within 2 hours of the visit time. Study product application (moisturizer only) will be performed under site supervision following Corneometer assessments at Day 2 (Visit 3), and TEWL and Corneometer assessments at Day 15 (Visit 4) There will be no product application at Day 29 (Visit 5). Last application will be by the subjects at home on the evening of Day 28±2 days.

During the treatment phase, TEWL will be measured at Areas 1 and 2 (face) and Areas 5 and 6 (legs) on Day 1 at baseline (pre-product application) and on Day 15 (Visit 4), and Day 29 (Visit 5). Moisturization will be measured at Areas 1 and 2 (face) and Areas 5 and 6 (legs) on Day 1 at baseline (pre-product application), 30 minutes and 6 hours post first supervised application, on Day 2 (Visit 3), Day 15 (Visit 4), and Day 29 (Visit 5).

These measurements have been included to objectively model skin moisturization and barrier function throughout the product use and regression periods of this study.

Protocol Number: 209638 Draft Clinical Protocol

The D-Squame physical challenge will be conducted at Areas 3 and 4 (face) and Areas 7 and 8 (legs) at Day 29 (Visit 5). These areas will be subject to the sequential application and removal of D-Squame adhesive discs; 3, 6, and 9 discs will be removed from the right and left side of the face and 4, 8, 12 discs removed from the right and left leg. TEWL will be measured prior to tape-stripping and after each set of 3 (face) or 4 (leg) discs. The amount of protein recovered by each disc will also be measured with a SquameScan device (Lu *et al*, 2014).

A regression period of 6 days during which subjects will only use the standard soap twice-daily on their face and lower legs will also start on Day 29 (Visit 5). Subjects will return their assigned study product at Day 29 (Visit 5).

During the regression phase, TEWL and moisturization will be measured at Areas 1 and 2 (face) and Areas 5 and 6 (legs) on Days 30, 31, 32, 33 and 34 (Visits 6-10).

Day 34 (Visit 10) is the final assessment day and subjects will exit the study after all procedures and assessments have been completed. The soap dish and diary cards will be returned at this visit.

Subject diary cards will be reviewed at each visit and missed, or additional applications will be recorded in the CRF.

Throughout the study, every effort will be made to ensure subject study site visits are scheduled for similar times of day for all subjects throughout the study. Subjects will be acclimatized to the environment of a controlled temperature (20-22°C) and relative humidity (40-60%) room for a period of at least 30 minutes before all TEWL and Corneometer measurements are conducted throughout the study (Berardesca *et al*, 1997)

4.2 Rationale for Study Design

A 5 to 7-day washout period is included to standardize product use across the study population prior to randomization. The standard soap will also be used throughout the study duration as a standard cleanser for all subjects to maintain a level of standard cleansing.

A 4-week study duration is selected to allow for at least one complete turnover of corneocytes in the stratum corneum. A 6-day regression period is included to evaluate any lasting effects on skin dryness and barrier function following 4 weeks twice daily usage.

TEWL assessments are included in this study to provide an objective measure of skin barrier function throughout the product use and regression periods of this study.

Corneometer assessments are included in this study to give objective measurements of skin moisturization throughout the product use and regression periods of this study.

The physical challenge is a minimally invasive and commonly used technique and consists of the consecutive removal of corneocytes, the cells which compose most of the SC and contribute to the barrier function of the skin, from the skin surface, using adhesive discs. The quantification of the amount of protein material removed from the SC using these adhesive discs provides a measure of the degree of adhesion of the corneocytes and therefore the strength of the skin barrier (Voegeli *et al*, 2007).

The inclusion of a regression period following the treatment period will be used to assess the lasting effects of the test product on the skin barrier function and moisturization, through TEWL and Corneometer assessment for up to 6 days after product application has stopped. Zhai and Maibach reported that a single application of a moisturizer does not cause long-lasting effects, but that repeated applications of a moisturizer (that is, two times a day for at least seven days)

Protocol Number: 209638 Draft Clinical Protocol

can result in a significant conductance increase for at least one week after application has ceased, demonstrating both short term and long-term benefits. (Zhai and Maibach, 1998)

The typical amount of body hair of male subjects makes objective instrumental assessments of moisturization and TEWL challenging, therefore, only female subjects will be recruited. To avoid confounding effects, subjects will be instructed to shave their legs (no other hair removal methods are permitted) on the first day of the washout phase and will not be permitted to shave their legs (or use any other hair removal process) at any other point during the study period until they exit the study.

There is a degree of heterogeneity between different areas of the body with regards to hair follicles, number of sebaceous and sweat glands and varying levels of exposure to sunlight and the resultant effects of ultraviolet (UV) radiation. While the study products have been designed to repair barrier function at all areas of the body, the magnitudes and variability of TEWL and Corneometer benefits at the face and leg are expected to differ.

4.3 Justification for Dose

The application quantity of the study products has been selected to reflect typical consumer usage of these types of products at approximately 2 mg/cm² (Simion *et al*, 2006). The first administration will be supervised by a trained technician when the subjects are at the study site.

An 8-hour minimum period between study product applications is required, except for Day 1, where measurements of TEWL and moisturization will be further taken at 24-hours following the first supervised application. Study product will be applied following completion of all assessments and measurements.

For the home-use period, after cleansing with the supplied standard soap, subjects will be instructed to apply 2 pumps of their assigned moisturizing cream to the allocated side of their face, including forehead and chin, twice-daily (in the morning and evening). Two pumps of moisturizing cream over the surface area of a typical half-face equates to approximately 0.6 mL or 2 mg/cm². In addition, after cleansing with the standard soap, subjects will be instructed to apply a further 6 pumps of their assigned moisturizing cream to the outside of the allocated lower leg, from the bottom of the knee to above the ankle, twice-daily (in the morning and evening). 6 pumps of moisturizing cream over the surface area of the outer side of a typical lower leg equates to approximately 1.8 mL or 2 mg/cm². This will be the same application quantities for the side of the face and leg when performed at the study site, but subjects will not use the soap cleanser when at the study site.

Subjects will be reminded that, as with all skin care products when topically applied to the face, care should be taken to avoid getting the products into the eyes. If contact does occur, then subjects will be instructed to rinse the eyes thoroughly with water.

4.4 End of Study Definition

A subject is considered to have completed the study if she has completed all phases of the study including the last visit or the last scheduled procedure shown in the Schedule of Activities.

The end of this study is defined as the date of the last subject's last visit.

Protocol Number: 209638 Draft Clinical Protocol

5 STUDY POPULATION

5.1 Type and Planned Number of Subjects

Healthy female volunteers aged 18 to 65 with self-reported dry and sensitive skin on their face and very dry skin on their legs will be recruited for this study.

The typical amount of body hair of male subjects makes objective instrumental assessments of moisturization and TEWL dryness challenging, therefore, only female subjects will be recruited.

Approximately 220 subjects will be screened to randomize approximately 150 and ensure at least 60 subjects for each treatment regimen complete the entire study.

This study can fulfill its objectives only if appropriate subjects are enrolled. The following eligibility criteria are designed to select subjects for whom participation in the study is considered appropriate. All relevant medical and non-medical conditions should be taken into consideration when deciding whether a subject is suitable for this clinical study.

Subject eligibility to participate in the clinical study should be reviewed and documented by an appropriate member of the investigator's study team before subjects are included in the study.

5.2 Inclusion Criteria

An individual must meet all of the following inclusion criteria to be eligible for enrollment into the study:

- 1. Subject provision of a signed and dated informed consent document indicating that the subject has been informed of all pertinent aspects of the study before any assessment is performed.
- 2. Subject is female who, at the time of screening, is between the ages of 18 and 65 years, inclusive.
- 3. A subject who is willing and able to comply with scheduled visits, the product application schedule, the Lifestyle Considerations, and other study procedures.
- 4. A subject in good general and mental health with, in the opinion of the investigator or medically qualified designee (if the investigator is not suitably qualified), no clinically significant/relevant abnormalities in medical history or upon dermatologist examination, or condition, that would impact the subject's safety, wellbeing or the outcome of the study, if they were to participate in the study, or affect the individual's ability to understand and follow study procedures and requirements
- 5. A subject who responds "Yes" to the following question: Do you consider yourself to have dry, sensitive skin on your face and very dry skin on your legs?
- 6. A subject with an overall dryness assessment total score of ≥3 for each side of the face at screening visit (Visit 1) and baseline visit (Visit 2). With no more than 0.5-unit score difference between each side of the face. Including an examiner score of at ≥ 1 (slight) for the roughness parameter (Appendix 1)
- 7. A subject with an overall dryness assessment total score of ≥6 for each leg at screening visit (Visit 1) and baseline visit (Visit 2). With no more than 1-unit score difference between each leg. (Appendix 1)
- 8. A subject with a Fitzpatrick skin type I-IV (Appendix 2).

Protocol Number: 209638 Draft Clinical Protocol

5.3 Exclusion Criteria

An individual who meets any of the following exclusion criteria will not be eligible for enrollment into the study:

- 1. A subject who is an employee of the investigational site, either directly involved in the conduct of the study or a member of their family; or an employee of the investigational site otherwise supervised by the investigator; or, a GSK CH employee directly involved in the conduct of the study or a member of their immediate family.
- 2. A subject who has participated in other studies (including non-medicinal studies) involving investigational product(s) within 30 days prior to study entry and/or during study participation.
- 3. A subject with, in the opinion of the investigator or medically qualified designee, an acute or chronic medical or psychiatric condition or laboratory abnormality that may increase the risk associated with study participation or investigational product application or may interfere with the interpretation of study results and, in the judgment of the investigator or medically qualified designee, would make the subject inappropriate for entry into this study.
- 4. A female subject who is pregnant (self-reported) or intending to become pregnant.
- 5. A female subject who is breastfeeding.
- 6. A subject with known or suspected intolerance or hypersensitivity to the study materials (or closely related compounds) or any of their stated ingredients.
- 7. A subject who, in the opinion of the investigator or medically qualified designee, should not participate in the study.
- 8. A subject with current or recent (within 6 months before the start of the study) history of atopic lesions and/or eczema.
- 9. A subject with a history of allergic reactions to topical-use products, cosmetics or medications or their ingredients.
- 10. A subject with any history of significant diseases or medical conditions known to alter skin or eye appearance or physiologic response (e.g. Type 2 diabetes) which could, in the opinion of the Investigator, preclude topical application of the investigational products and/or interfere with the evaluation of the test site reaction.
- 11. A subject presenting open sores, pimples, or cysts at the application site (face or lower legs).
- 12. A subject with an active dermatosis (local or disseminated) that might interfere with the results of the study.
- 13. A subject currently using any medication which in the opinion of the investigator, may affect the evaluation of the investigational product, or place the subject at undue risk
- 14. A subject who has used any of the following topical or systemic medications up to 1 month before the screening visit or intends to use during the study period: immuno-suppressants, antihistamines, non-steroidal anti-inflammatory drugs (NSAIDS), and corticosteroids.
- 15. A subject who has used oral or topical treatment with vitamin A acid and/or its derivatives up to 1 month before the screening visit or intends to use during the study period.
- 16. A subject who intends to use any topical drug or medication on the proposed application areas.

Protocol Number: 209638 Draft Clinical Protocol

17. A subject who has been vaccinated up to 1 month before the screening visit or is intending to receive a vaccination during their participation in the study.

- 18. A subject currently receiving allergy injections, or received an allergy injection within 7 days prior to Visit 1, or expects to begin injections during study participation
- 19. A subject with a recent history (within the last 5 years) of alcohol or other substance abuse.
- 20. A subject with any skin marks on the face or lower legs that might interfere with the evaluation of possible skin reactions (e.g. pigmentation disorders, vascular malformations, scars, tattoos, excessive hair, numerous freckles).
- 21. Subjects with corneal ulcers, keratoconus, blepharitis, meibomitis, pterygium, chemosis, moderately or severe hyperemia or other active ocular diseases.
- 22. A subject who has previously been enrolled in this study.
- 23. A subject who is unwilling to abstain from smoking tobacco or using any other nicotine-containing products.
- 24. A subject with visible sunburn on any of the test sites.
- 25. A subject with moles, tattoos, scars, hairs, etc. at the test areas if it is likely that they could affect the assessments.
- 26. A subject who has used self-tanning products on the test areas (face and arms) within 2 weeks prior to the screening visit.
- 27. A subject who intends to expose their skin to natural or artificial ultraviolet (UV) light (e.g. sunbathing or tanning beds).
- 28. A subject with any subject self-assessed or dermatologist dryness parameter score 4 (very severe) on the test areas of the lower legs or face (Appendix 1).
- 29. Any subject who, in the judgment of the Investigator, should not participate in the study.

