5.5 Lifestyle Considerations

During the entire study (screening – Visit 10) the following restrictions apply:

Subjects may be asked to remove their facial make-up at the screening visit to allow for the visual assessments to be made.

Subjects will not be permitted to use any other skin care products, including but not limited to: leave-on cosmetics, moisturizers, lotions, creams, sunscreens, soaps, cleansing, exfoliation products, etc. on their face or legs, other than the standard soap and study product(s) provided.

At all post baseline study visit days, subjects must cleanse their face and legs with the standard soap and then apply the test product (s) approximately 10-16 hrs before each study appointment (i.e. evening before).

No use of any product on the face or legs, including the standard soap and test product, within 10 hours of all instrumental measurements on visit days (no showering/bathing permitted with soaps/shampoo within this period) will be permitted.

Protocol Number: 209638 Draft Clinical Protocol

Subjects will be permitted to wash their face and legs with water only on the day of site visit. However, on the day of site visit, subjects should not wash their face or legs less than 2 hours before the first instrumental measurement is taken.

On site visit days for visits 2 and 4, the morning product application will be performed at the site after all assessments have been completed. The second application on each of the days will be performed by the subjects at home approximately 8-12 hours following the on-site application.

There should be no introduction of new products during the study including but not limited to soap, laundry detergent, or fabric softener.

Subjects should avoid wearing tight or restrictive clothing on, or around the face or over the legs.

Chemical or physical hair removal methods or bleaching or dying of the hair on the face and legs is not permitted during the study. To avoid confounding effects, subjects will be instructed to shave their legs on the first day of the washout phase and will not be permitted to shave their legs (or use any other hair removal process) at any other point during the study period until they exit the study. Subjects may use the soap provided to create a lather to shave their legs on the first day of the washout period.

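### Exclusion 26 applies the self-tanner look-back to the face and arms, whereas the study's test areas are the face and lower legs

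*Protocol*

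**What the plan says.** Exclusion 26 (Protocol 5.3) removes "A subject who has used self-tanning products on the test areas (face and arms) within 2 weeks prior to the screening visit". The parenthesis tells the site which test areas are meant.

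The rest of the protocol gives different sites. Section 4.1 states: "The chosen application sites are the face and the lower legs". It adds: "A total of 8 areas will be assigned to each subject". Areas 1 to 4 are on the face. For the legs, "Area 5 (right leg) and 6 (left leg) will be the site used for leg TEWL and Corneometer assessments throughout the treatment phase", and "Area 7 (right leg) and 8 (left leg) will be the site used for the leg tape-strip challenge at Day 29". SAP 1.1 repeats this layout.

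The same exclusion list also names the legs elsewhere: in exclusion 11 ("A subject presenting open sores, pimples, or cysts at the application site (face or lower legs"), in exclusion 20, and in exclusion 28 ("on the test areas of the lower legs or face (Appendix 1").

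Section 5.5 bars other skin care products on the face or legs, but only from the screening visit onward: "During the entire study (screening – Visit 10) the following restrictions apply".

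**The concern.** This is an operative eligibility rule that site staff must apply and document, so a wrong body site has two consequences.

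The first is over-exclusion. A subject who used self-tanner only on her arms fails screening for a reason unrelated to anything measured. Under section 5.6 a screen failure cannot be screened again, so she is lost to the study.

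The second is under-exclusion. The sponsor evidently thought a two-week look-back worth having for skin that will be measured, yet the criterion omits one of the two measured sites. A subject with recent self-tanner on her legs can enter. Residual product could be present when the legs are graded for eligibility at screening, and possibly when the Day 1 leg TEWL and Corneometer baselines are taken.

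**Working it through.** The plan gives no figure to reproduce. The check compares the sites named, looks for another rule that closes the gap, and works through the protocol's own timings.

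**1. Sites named**

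| Place | Sites |
|---|---|
| Protocol 4.1, application sites | face, lower legs |
| Protocol 4.1 and SAP 1.1, Areas 1–8 | four on the face, four on the lower legs |
| Exclusions 11, 20, 28 | face, lower legs |
| Exclusion 26 | face, arms |

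Exclusion 26 covers one of the two real test sites, omits the other, and adds one that is not a test site.

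**2. Does another rule cover past self-tanner use on the legs?**

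- Exclusion 16 concerns intended use of a topical drug or medication, not past cosmetic use.
- Exclusions 20 and 25 concern marks, scars, tattoos, moles and hair.
- The product ban in section 5.5 starts at screening and does not look back.
- Exclusions 7 and 29 give the investigator general discretion, but nothing in them prompts a question about leg self-tanner.

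None of these sets a look-back for the legs.

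**3. Time from last permitted use to the Day 1 baseline**

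Inputs: a look-back of 14 days before screening (exclusion 26) and a washout of 5 to 7 days (section 4.1).

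- Face: at least 14 + 5 = 19 to 14 + 7 = 21 days.
- Legs, literal reading, with use the day before screening: 1 + 5 = 6 to 1 + 7 = 8 days.

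In this example the legs have 13 days less than the face (19 − 6 = 21 − 8 = 13).

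**4. Time from that same use to Day 29**

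Day 1 to Day 29 is 28 days, with a window of ±2 days (Schedule of Activities), so 26 to 30 days. Adding step 3 gives 6 + 26 = 32 to 8 + 30 = 38 days. Section 4.2 says that 4 weeks allows at least one complete turnover of corneocytes.

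**5. Which leg analyses use the Day 1 value**

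- Change from Day 1: TEWL at Days 15, 29 and 30–34 (1 + 1 + 5 = 7), and Corneometer at 30 minutes, 6 hours, 24 hours, Days 15, 29 and 30–34 (3 + 2 + 5 = 10). Total 17.
- No Day 1 value: challenge TEWL at three disc counts, measured against a Day 29 pre-challenge baseline (SAP 3.1), and total protein, analysed without a baseline covariate (SAP 4.5.1). Total 3 + 1 = 4.

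So 17 of 21 leg analyses use the Day 1 leg baseline. This shows where an effect could reach; it does not estimate how many analyses would be disturbed.

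**The case against.** The best defence is that this is a slip of wording. The operative term is the test areas, which the protocol defines correctly elsewhere, and a sensible site would apply the term and ignore the faulty parenthesis. That may well happen. But staff would then be departing from the written criterion, and SAP 4.1.2 lists eligibility criteria among the possible categories of important deviation.

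Other safeguards narrow the gap. Only soap is used on the legs during washout, the legs are shaved on its first day, and each leg must score at least 6 for dryness, with the legs within 1 unit of each other, at both screening and baseline. These points stand as mitigation. None of them asks about use before screening.

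The consequence for inference is also limited. Success rests on facial TEWL at Day 29, and exclusion 26 does cover the face. The leg endpoints are secondary and played no part in the sample size (Protocol 12.1). Treatment side is randomized and the side-specific baseline is a covariate, so use on both legs alike largely cancels in the left/right comparison.

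A reader might infer that every leg endpoint is compromised: 21 of the 41 secondary endpoint-by-time-point analyses, since the face contributes 6 + 10 + 3 + 1 = 20. The documents do not support that. The four tape-strip and protein analyses use no Day 1 value and come after about one corneocyte turnover. For the other 17, neither document says that self-tanner changes the readings, by how much, or how many subjects use it on their legs.

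**Conclusion.** The contradiction is in the current text, and no other rule resolves it. Exclusion 26 must be reconciled with section 4.1 and exclusion 28.

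The effect is bounded. The primary endpoint is untouched. The plausible reach is leg dryness grading at screening, the Day 1 leg TEWL and Corneometer baselines, and early leg readings. The expected form is added noise rather than side bias, and its size cannot be stated because the documents give neither the frequency of use nor the shift in readings. The number of subjects wrongly rejected for arm use is unknown for the same reason.

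Three assumptions underlie this: that sites follow the parenthesis as written; that self-tanner use is usually similar on both legs; and that the corneocyte turnover cited in section 4.2 also removes most of any self-tanner effect by Day 29. The last is an inference from the protocol's statement and is not itself stated there.

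**What to change.** In exclusion 26, change the parenthesis from face and arms to face and lower legs, so that it agrees with section 4.1 and exclusion 28. Make the same change in the screening checklist. The look-back period and the rest of the criterion can stay as they are.

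The cost is a minor amendment. It changes one site name but, under section 13.3.1, needs ethics committee approval before use. No change to the design, sample size or analysis is required. If subjects have already been screened under the present wording, record which reading the site applied.
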